## G. Safety and Adverse Events

### **G1. Definitions**

Adverse Events (AE) would include a data breach in this study.

Serious Adverse Events (SAE) are defined as any medical occurrence that results in death, is life threatening, requires inpatient hospitalization, results in persistent or significant disability, is a congenital anomaly or birth defect, or is an event requiring medical intervention to prevent any of these examples of an SAE. SAEs may be mild (transient, easily tolerated by participant), moderate (causes discomfort or interrupts the study or the participant's usual activities), or severe (causes considerable interference with usual activities).

### **G2. Reporting of Adverse Events**

In the study, all adverse events, whether expected or unexpected, will be reported to Washington University's Human Research Protection Office (HRPO) [see Appendix 6. Adverse Events Log]. The HRPO office will be notified of any serious adverse experience within ten working days of the occurrence. If the event is fatal or life threatening, HRPO will be notified immediately, but not more than twenty-four hours after occurrence. Other adverse events will be reported to HRPO in annual reports. Adverse events will be reported from the time of participant enrollment to four months post-enrollment.

In the case of a data breach, Information Security (IS) will be notified immediately and the IS security date and number will be recorded. Participants will be notified by a phone call from the research coordinator.

### **G3. Data Collection Procedures for Adverse Events**

In cases where the principal investigator deems it necessary for a participant to stop receiving the intervention prior to end point (e.g. change in health rendering patient unable to participate), data will be included up to the date of the event.

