### **C2. Outcomes of Interest**

- Primary: Time to attending a follow-up visit with referred primary or specialty care within 120 days post-discharge
- Secondary:
  - Time to re-visit to the ED (BJH or other) within 120 days post-discharge.
- Tertiary:
  - Patient engagement levels with the intervention: number of successful attempts to reach participant, number of successful attempts to schedule a follow-up appointment, length of phone call to schedule an appointment, and number of successful follow-up appointments with a specialist provider versus a primary care provider.

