#### **E2. Data Analysis, Sample Size Estimation, and Study Power**

The sample size from the trial was determined to meet criteria to be sufficiently powered at 90% for a two-sided  $\alpha = 0.05$ , for a 10% improvement of the primary outcome. We will conduct an Intention-to-Treat analysis to test the impact of the intervention on participant follow-up attendance and ED re-admissions. We will also conduct descriptive statistics regarding user engagement.

We might experience missing outcome data if a participant set up a follow-up appointment with a provider who was not their referral provider and is not a part of the BJH EMR network or Missouri Health Connection. These appointments will not be accessible to our study team and a participant may be labeled as *non-compliant* erroneously; however, since most Missouri health clinics participate in the Missouri Health Connection, this issue will be rare and should apply to both the control and intervention arm equally.

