### ***B2. Eligibility Criteria***

#### Inclusion criteria:

1. 18 years and older.
2. Accessible SMS capable mobile phone or residential landline.
3. Able and willing to provide consent and authorize access of participant medical record for study use.
4. Able to read English or have English-speaking family member to assist with phone communications.
5. Supplied a clinical referral with recommended outpatient follow-up timeframe or date within 4 months of discharge.

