#### ***B6. Randomization Method and Blinding***

Once a participant is added to the Intervention Builder account, the integrated software independently randomizes participants to either the control or the intervention arm. The software s randomly allocates participants in a 1:1 ratio to intervention and control arms.

Even though participants are not informed if they were enrolled in the intervention or control arm, they are capable of inferring this information (if they did or did not receive a text or phone call).

Treating clinical staff are blinded to arm allocation. They complete treatment before a participant enrolls in the study.

The research team will be blinded to arm allocation whenever possible. EMR review to identify attended follow-up appointments and ED re-visits will be completed before intervention responses are reviewed and analysis commences.

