## C. Study Procedure

### **C1. Intervention Treatment**

After providing written informed consent, participants in the intervention arm begin receiving text or voice messages to help them schedule a follow-up appointment with the referral provider per the pseudocode template attached [see Appendix 5. Pseudocode]. By default, participants receive automated messages starting one hour following discharge if it is normal business hours (Monday through Friday 0900 to 1700), or at 1000 the next business day if they are discharged outside of normal business hours. Automated messages are sent up to three days in a row or until the participant responded or the participant opted out, whichever occurs first. The participant is able to respond to all messages by either using alphanumeric (1-3) or binary answers (Yes or No). The primary goal of the intervention is to connect the participant directly to the referral provider's office to schedule an appointment. Once the participant hangs up with the office, the intervention asks if they were successful with scheduling an appointment.

If the participant fails to respond to the intervention, the intervention leaves a voicemail detailing instructions on how to reach the referral provider's office via a toll-free phone number. This toll-free number is the same number that showed up on the participant's cell phone or landline caller ID when the intervention reached out to them. If the participant calls the toll-free number, the intervention works as it normally would.

Once an appointment is made, the system sends reminders at 14 days, 7 days, 3 days, and 1 day before the appointment date. The day after the appointment, the intervention contacts the participant to see if they attended it. If the participant did attend, the intervention stops. If the participant did not attend and needs to reschedule, the intervention resets and starts over again.

Participants can voluntarily opt-out of receiving any further messages at any time if they text STOP or if they press \* on the keypad during an automated phone message.

Participants in the control arm do not receive any messages.

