#### **F. Data Collection and Analysis**

##### **F1. Outcome Assessments**

The outcomes of interest are:

- Primary: Participant follow-up attendance to a referral clinic or provider (compliant / non-compliant).
- Secondary:
  - Number of re-admissions to the ED (BJH or other) within 30 days and again within four months post-discharge.
- Tertiary:
  - Patient engagement levels with the intervention: number of successful attempts to reach participant, number of successful attempts to schedule a follow-up appointment, length of phone call to schedule an appointment, and number of successful follow-up appointments with a specialist provider versus a primary care provider.

To minimize bias, all clinical staff and research team members conducting patient chart reviews will be blinded to participant arm allocation [see Section B6. Randomization Method and Blinding]. We anticipate the study will have no impact on clinical workflow since the intervention will take place during a gap in clinical care when a participant is transferred between providers and we will only be completing patient chart assessments and data analysis to finalize the study.

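### G3 cuts a participant's data at the event that stops the messages; as worded this can happen only in the intervention arm, does not fit the intention-to-treat analysis, and can lower that arm's ED re-admission count

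*Combined protocol and SAP*

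**What the plan says.** Section G3 covers participants whom the principal investigator takes off the intervention before the end point. Its example is a "change in health rendering patient unable to participate". For them, "data will be included up to the date of the event".

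Other sections bear on this rule:

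- **Who can be stopped.** Section C1: "Participants in the control arm do not receive any messages".
- **How the data are to be analysed.** Section E2: "We will conduct an Intention-to-Treat analysis to test the impact of the intervention on participant follow-up attendance and ED re-admissions".
- **Where outcomes come from.** Section B6: "EMR review to identify attended follow-up appointments and ED re-visits will be completed before intervention responses are reviewed". The inclusion criteria in B2 require participants to "authorize access of participant medical record for study use".
- **What is counted.** F1 gives the secondary outcome as "Number of re-admissions to the ED (BJH or other) within 30 days and again within four months post-discharge". C2 gives it as "Time to re-visit to the ED (BJH or other) within 120 days post-discharge".
- **Withdrawal.** B9 has its own rule for participants who withdraw: data up to withdrawal are analysed. It applies in either arm.

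G3 does not say whether its data are chart outcomes or only message responses. It also leaves open whether the cut-off is the date of the health change or the date the messages stop. No section states that chart outcomes continue after a stop.

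**The concern.** The trigger in G3 is the stopping of an intervention that only one arm receives. A control participant with the same change in health stays under observation to day 120, and every later ED visit counts. An intervention participant who is stopped has later visits left out. The arms then differ in observation time for a reason created by the data rule, and the reason is related to health. An intention-to-treat comparison is meant to exclude exactly this.

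The effect differs by outcome:

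- **Number of ED re-admissions (F1).** Leaving out later visits in one arm can only lower that arm's count. This is the direction of the second hypothesis in B2 of the protocol part.
- **Time to re-visit (C2).** The cut acts as censoring in one arm. It favours the intervention if stopped participants have higher later risk, and works against it if their risk is lower.
- **Attendance (primary).** The sign depends on whether stopped participants are dropped or scored as non-compliant.

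**Working it through.** **The plan's own figure.** F4 needs 266 participants and allows 20% loss: 266 / (1 − 0.20) = 332.5, rounded up to 333. This reproduces. With 1:1 allocation (B6) an arm has 333 / 2 = 166.5, or about 166. So 1% of an arm is about 2 people, 5% about 8 and 10% about 17.

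The documents give no stop rate, no ED re-visit risk and no stop times. All of these are assumptions below.

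**1. Share of the intervention arm with a counted re-visit.** Assume stopped participants have a 60% chance of a re-visit by day 120 and a constant hazard h = −ln(0.40) / 120 = 0.00764 per day. If a share p of the arm is stopped at day s, the share lost is

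p × [mean of exp(−h·s) − exp(−120h)], with exp(−120h) = 0.40.

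The mean of exp(−h·s) is 0.894 for stops uniform over days 0–30 and 0.655 over days 0–120. For p = 5%: 0.05 × (0.894 − 0.400) = 0.0247 and 0.05 × (0.655 − 0.400) = 0.0127. The upper bound, with all stops on day 0, is p × 0.60.

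| Share stopped | Stops over days 0–30 | Stops over days 0–120 | Upper bound |
|---|---|---|---|
| 1% | 0.5 points | 0.3 points | 0.6 points |
| 5% | 2.5 points | 1.3 points | 3.0 points |
| 10% | 4.9 points | 2.5 points | 6.0 points |

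**2. Number of re-admissions, the form in F1.** Assume 166 in the arm, a constant rate equivalent to 30% risk over 120 days, and all stops at day 30, so that 90/120 = 0.75 of the window is removed. Without truncation the expected count is 166 × (−ln 0.70) = 59.2. If 5% are stopped and their rate is average, the loss is 166 × 0.05 × 0.357 × 0.75 = 2.2, or 3.7%. If their rate doubles after stopping, the full count is 59.2 + 2.2 = 61.4, the loss is 4.4, and 57.0 remain (−7.2%). For 2% and 10% stopped, the falls are 1.5% and 7.5% at the average rate, and 3.0% and 14.0% at the doubled rate. These percentages do not depend on the 30%.

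**3. Time to re-visit, the form in C2.** Treat stopped participants as censored, with an overall 120-day risk of 30%. The figures are the large-sample change in the Kaplan–Meier 120-day risk for a mixture of stopped and other participants.

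| Share stopped | Their 120-day risk | Stops over days 0–30 | Stops over days 0–120 |
|---|---|---|---|
| 5% | 60% | −1.3 points | −0.7 points |
| 1% | 60% | −0.3 points | −0.1 points |
| 5% | 20% | +0.5 points | +0.3 points |

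**4. Attendance.** Assume 5% are stopped and attend at 10%, and the other 95% attend at 30%. The true rate is 0.95 × 0.30 + 0.05 × 0.10 = 29.0%. Dropping the stopped participants gives 30.0%. Scoring them all non-compliant gives 0.95 × 0.30 = 28.5%.

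With chart review to day 120 for everyone randomised, each of these distortions is zero.

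**The case against.** The strongest reply is that G3 need not govern chart outcomes at all. It is one sentence in the adverse-event section. E2 names intention-to-treat for exactly these two outcomes, C2 and F1 set follow-up windows with no exception for stopped messages, and B6 and F1 have charts reviewed blind. A blinded reviewer cannot cut a chart at a date that exists in one arm only.

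The ambiguity is real, but the other readings do not remove the problem. If the clause means adverse-event data, it conflicts with G2, which reports events to four months, and with G4, which follows serious events to resolution or stabilisation. If it means message responses, it does almost nothing, since few or none follow once messages stop. Blinded review does not cancel a stated inclusion rule: a cut made during review could reveal the arm, and a cut made later would discard outcomes already collected. Nothing says whether E2 or G3 prevails.

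The second reply is that stops will be rare, and this largely stands. G3 covers only stops by the investigator, not opt-outs. B7 and D4 provide no follow-up communication and no alerts, D3 has the system request no health information, and C1 makes the message sequence short for many participants. Nothing in the documents supports 5% or 10%. At 1% the loss is 0.3 to 0.5 points, less than one person in 166, whereas the standard error of a difference at 30% risk is about √(2 × 0.30 × 0.70 / 166) = 5 points.

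The third reply is that G4 lets some participants discontinue the study after a serious event. G4 gives no rule for outcome data, so analysing those participants as randomised agrees with E2.

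**Conclusion.** The concern holds. Followed as written, G3 truncates data in the intervention arm only, for health-related reasons, against the intention-to-treat commitment in E2 and without need, because the outcomes come from charts. The direction is certain only for the number of ED re-admissions, where the cut can only lower the intervention arm's count.

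The size is uncertain because every input beyond the arm size is assumed. It is probably small if stops are rare: about half a point or less at 1% stopped, and 1.3 to 2.5 points at 5% with a 60% re-visit risk. The change should be made because the rule is one-sided and cheap to correct, not because a large bias has been shown. Confidence is medium, mainly because G3 does not say which data it means.

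**What to change.** Replace the data clause in G3 with: *Stopping messages does not end outcome follow-up. Attendance and ED re-visits are taken from chart review to day 120 for every randomised participant in both arms and analysed as randomised, except that participants who withdraw from the study under B9 contribute data up to withdrawal.*

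This also settles which data G3 refers to, and it covers participants who discontinue under G4 without withdrawing under B9. It leaves unchanged when and why messages are stopped, and B9 stays as it is.

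The cost is one clause and chart review to day 120 for the few participants whose messages are stopped. No participant contact and no change in sample size is needed.

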#### **G4. Follow-up of Serious Adverse Events**

All SAEs will be followed until resolution, permanent outcome of the event or until stabilization. Some SAEs will require study discontinuation. For example, participants will discontinue the study if they are unable to tolerate study participation. These participants will continue to undergo follow-up evaluation by the investigator, direct consultation between the investigators and the treating physicians and establishment of ongoing care plans before being discharged from the study. For participants experiencing an SAE that does not require study discontinuation, continuing study participation will require discussions of the potential risks and benefits of continuing participation, involving the participant and their treatment team, the investigators and the participant's treating physicians.

#### **H. Risks and Benefits**

Potential risks include possible breach of confidentiality involving PHI/study data and possible risk of annoyance by the subject due to repetition of messages.

Efforts will be dedicated to minimize the risk of breach of privacy. All patient information and study data will be password protected in computer files and all paper forms will be kept in a secure locked office within a locked suite, controlled by the research staff. Additionally each patient will be assigned a study ID number to minimize risk of exposure of patient information. The ID number will be used to code all the data assigned to each patient as they are included sequentially into the study. This number will be used for the electronic spreadsheet and placed on the paper documents (if created) and a list of the assigned numbers will be maintained in a password-protected electronic spreadsheet.

Communication via phone and text are unsecured and potentially non-confidential. Additionally the information stored on a patient's phone is outside the control of the study investigator. The patient was informed of these risks and was required to consent to exchange potential Protected Health Information (PHI) via these communication lines to participate in the study. To prevent the accidental disclosure of PHI from pop-up phone notifications, the text message read: "Confidential message" and the content began 3 lines later, which was not seen on an automatic notification preview [see Appendix 8. Text Message Example Screenshots].

The major side-effect of this intervention is potential annoyance and disruption to patient lives. To reduce these risks, text messages and phone calls are reduced to the minimum possible to meet reminder or patient communication guidelines. In addition, efforts are made to ensure that the text message and phone calls are kind, courteous, respectful, and timely. Patients are also given the opportunity to opt out at any time via a "STOP" message or the \* dial key.

##### **I2. Key Personnel Training Certification**

All research team members complete Washington University HIPAA and CITI training courses. They are also registered with the Washington University Human Research Protection Office at myIRB.wusm.wustl.edu and added to the study's research team prior to viewing PHI.

**13. Funding Source and Conflicts of Interest**

This study was supported by the NIH/National Center for Advancing Translational Sciences (NCAT), grant ULI TR000448. Epharmix/CareSignal, Inc is also providing in kind services that allows us to create a free account for this study on the Epharmix/CareSignal Intervention Builder platform where we can design and build our own unique intervention. Automated phone or text messages that we send out from our account are free of charge to the study, as well as the phone responses that participants send back to our account. Phone companies may still charge participants for their responses based on participants' individual data and phone plans. These charges are outside of our control.

**14. Subject Stipends or Payments**

No payment or reimbursement is offered for this study.

## 2. Demographic Survey

Interview occurred:  In person  
 Over the phone

Date: \_\_\_\_\_

### Demographics

Name: \_\_\_\_\_

Date of birth(MM/DD/YYYY): \_\_\_\_\_

Gender (check):  Male  Female

#### Race (check all that apply):

- White
- Black or African American
- Asian
- American Indian or Alaskan Native
- Native Hawaiian or Pacific Islander
- Other \_\_\_\_\_
- I decline to answer

#### Ethnicity:

- Hispanic or Latino
- Not Hispanic of Latino
- I decline to answer

#### What is your highest level of education?

- No formal education
- Grade school
- Some high school
- High school graduate or GED
- Some college
- College graduate or associate's degree
- Some graduate school
- Graduate degree or professional degree
- I decline to answer

#### Marital status:

- Never married
- Married
- Domestic partnership
- Separated
- Divorced
- Widowed
- I decline to answer

### Physical health

#### Do you have any other medical problems?

##### Please check all the apply:

- Diabetes mellitus
- Hypertension/high blood pressure
- Heart disease (heart attack, coronary artery disease, arrhythmias, valve disease)
- Neurological disease (including previous stroke, seizures, fainting)
- Lung disease (COPD, emphysema)
- Thyroid disease
- Cancer
- Other: \_\_\_\_\_
- I decline to answer

#### 4. Pilot Study Timeline

# 5. Pseudocode

7. Security Clearance

## Information Security Office IRB Study Security Report

### \*\*\* IRB Study Security Report \*\*\*

Date:	06/09/2015	Security Event ID:	20140131-01
Protocol:	IRB ID #: 201504079 Title: E-interventions and medical care		
Risk Rating:	 Low  Med  High  Critical  Not Yet Rated		
Requested By:	[name]		
Status:	Approved		

### Event Type

 Transmission of PHI	 Third Party Review	
 Secure Storage	 Social Media Review	 Other (explain below)
 Process Review		Other:

### Review Notes

Background	
In addition to the scan we will need the following information to begin the assessment:
 
 
Study Number and/or Name ( IRB ID #: 201504079 Title: E-interventions and medical care)
 
Identify what ePHI (electronic protected health information) data elements you will be collecting, storing or transmitting
 
 
We will be collecting and storing name and phone number. These will not be transmitted.
 
 
Identify where the ePHI will be created, stored or
 

-------------------	--

## Information Security Office IRB Study Security Report

transmitted (network share, workstation, laptop, USB drive, external site)

On the network server at [epx.wustl.edu](http://epx.wustl.edu).

4. How is the ePHI protected (password protected document, encrypted USB Drive, Secure Transmission)

Password protected site at [epx.wustl.edu](http://epx.wustl.edu)

5. Are you using social media for outreach

No.

6. Will the information be stored on a WUSM supported device

[Epx.wustl.edu](http://Epx.wustl.edu) is hosted on WU servers

In addition the database will store the date and time patients respond to outgoing automated phone call and text messages (using messages that have no PHI per review by [name], WU HIPAA compliance officer ). The system will store their responses, which can only be numerical or binary, but relate to health events, such as pain, glucose, or blood pressure measurements.

This information won't be transmitted but should be stored in an encrypted fashion on the server.

The password in the database is hashed and encrypted using the blowfish algorithm, so that it's not reversible. In addition the

